### 6.7 3 Months Phone Follow-Up

- For subjects in the WaveCrest arm, if the LAA was closed at 45 days, instruct subject to discontinue clopidogrel but to continue aspirin at the assigned dosage.
- If the LAA was not closed at 45 days, clopidogrel may be continued at Investigator discretion until flow  $\leq 5$ mm is noted in a subsequent TEE.
- Record cardiac medications, including antiplatelet and anticoagulant medications.
- Record adverse events, device malfunctions, and protocol deviations as appropriate.

### 6.8 Follow-up 6 Month Office Visit

- Perform physical exam
- Administer QoL questionnaire (see **Quality of Life Questionnaire - SF-36**)
- Qualified trial personnel who are blinded to subject's randomization and implanted device administer the QVSFS (see **Appendix III: Questionnaire for Verifying Stroke-Free Status**); If the subject has experienced symptoms resulting in a QVSFS score  $> 0$  since their most recent follow-up, a board-certified study Neurologist blinded to subject's randomization and implanted device, to the extent possible, must evaluate the subject or otherwise provide rationale for why an in-person neurology visit and exam are unnecessary. This **Unscheduled Neurology Visit** must be completed within 14 days of the QVSFS administration or site's awareness of the onset of stroke symptoms. (See **Section 6.12** for details of Unscheduled Neurology Visit)
- For subjects in the Watchman arm, if the LAA was closed at 45 days, clopidogrel may be discontinued per the product DFU but aspirin should continue per the product DFU.
- If the LAA was not closed at 45 days and the subject remains on warfarin (Watchman arm) or DAPT (WaveCrest arm), a TEE should be repeated at this visit. Discontinuation of warfarin (Watchman arm) or P2Y12 inhibitor (WaveCrest arm) is at physician discretion but is recommended if peri-device color Doppler flow demonstrated by TEE is  $\leq 5$ mm.
- If an adequate seal is not demonstrated, warfarin (Watchman arm) or P2Y12 inhibitor (WaveCrest arm) may be continued at Investigator discretion until flow  $\leq 5$ mm is noted. Watchman subjects who continue warfarin for 6 months post-implant are not required to start clopidogrel but should remain on aspirin per the product DFU.
- Sites that routinely perform a 6-month TEE as their standard of care (SOC) may perform a TEE in all subjects at that site. This is not required for sites that do not perform a 6-month TEE as part of their SOC.
- Evidence of device thrombus is recommended to be treated with a 6-week course of warfarin (+/- aspirin) and repeat TEE.
- Record cardiac medications, including antiplatelet and anticoagulant medications
- Record adverse events, device malfunctions and protocol deviations as appropriate

	Title: The WAVECREST 2 Trial  Clinical Investigational Plan	Doc. #: CHX_IP014	Rev: H
---	--	-----------------------------	------------------

## 6.9 Follow-up 1 Year Office Visit

- Perform physical exam
- Administer QoL questionnaire (see **Quality of Life Questionnaire - SF-36**)
- Qualified trial personnel who are blinded to subject’s randomization and implanted device administer the QVSFS (see **Appendix III: Questionnaire for Verifying Stroke-Free Status**); If the subject has experienced symptoms resulting in a QVSFS score > 0 since their most recent follow-up, a board-certified study Neurologist blinded to subject’s randomization and implanted device, to the extent possible, must evaluate the subject or otherwise provide rationale for why an in-person neurology visit and exam are unnecessary. An **Unscheduled Neurology Visit must be completed** within 14 days of QVSFS administration or site’s awareness of the onset of stroke symptoms. (See **Section 6.12** for details of Unscheduled Neurology Visit)
- Perform a TEE following the Echocardiography Protocol and submit images to ECL
- If an adequate LAA seal is observed, instruct subject to remain on aspirin dosage as assigned daily indefinitely. Table 3 summarizes the post-procedure anticoagulation and antiplatelet regimen for the duration of trial follow-up.
- If an adequate seal is not demonstrated, warfarin (Watchman arm) or P2Y12 inhibitor (WaveCrest arm) may be continued at Investigator discretion and/or until flow  $\leq$  5mm is noted.
- Evidence of device thrombus is recommended to be treated with a 6-week course of warfarin (+/- aspirin) and repeat TEE.
- Record cardiac medications, including antiplatelet and anticoagulant medications
- Record adverse events, device malfunctions and protocol deviations as appropriate

## 6.10 Follow-up 2 Year, 3 Year, 4 Year and 5 Year Office Visits

At each of the above office visits:

- Perform physical exam
- Administer QoL questionnaire (see **Quality of Life Questionnaire - SF-36**)
- Qualified trial personnel who are blinded to subject’s randomization and implanted device administer the QVSFS (see Appendix III: Questionnaire for Verifying Stroke-Free Status). If the subject has experienced symptoms resulting in a QVSFS score > 0 since their most recent follow-up, a board-certified study Neurologist blinded to subject’s randomization and implanted device, to the extent possible, must evaluate the subject or otherwise provide rationale for why an in-person neurology visit and exam are unnecessary. An **Unscheduled Neurology Visit must be completed** within 14 days of QVSFS administration or site’s awareness of the onset of stroke symptoms. (See **Section 6.12** for details of Unscheduled Neurology Visit).
- Instruct subject to remain on daily aspirin at assigned dosage indefinitely. Table 3 summarizes the post-procedure anticoagulation and antiplatelet regimen for the duration of trial follow-up.

	Title: The WAVECREST 2 Trial  Clinical Investigational Plan	Doc. #: CHX_IP014	Rev: H
---	--	-----------------------------	------------------

- If an adequate seal was not demonstrated at the 1-year TEE, warfarin (Watchman arm) or P2Y12 inhibitor (WaveCrest arm) may be continued at Investigator discretion.
- Evidence of device thrombus is recommended to be treated with a 6-week course of warfarin (+/- aspirin) and repeat TEE.
- Record cardiac medications, including antiplatelet and anticoagulant medications
- Record adverse events, device malfunctions and protocol deviations as appropriate

### 6.11 Follow-up Phone 1.5 Year, 2.5 Year, 3.5 Year and 4.5 Year

The QVSFS must be administered over the phone by blinded trial personnel (see **Appendix III: Questionnaire for Verifying Stroke-Free Status**)

If the subject has experienced symptoms resulting in a QVSFS score > 0 since their most recent follow-up, a Neurologist blinded to subject’s randomization and implanted device, to the extent possible, must evaluate the subject or otherwise provide rationale for why an in-person neurology visit and exam are unnecessary. An **Unscheduled Neurology Visit** must be completed within 14 days of QVSFS administration or site’s awareness of the onset of stroke symptoms. (See **Section 6.12** for details of **Unscheduled Neurology Visit**)

- Instruct subject to remain on daily aspirin at the assigned dosage indefinitely. Table 3 summarizes the post-procedure anticoagulation and antiplatelet regimen for the duration of trial follow-up.
- If an adequate seal was not demonstrated at the 1-year TEE, warfarin (Watchman arm) or P2Y12 inhibitor (WaveCrest arm) may be continued at Investigator discretion.
- Record cardiac medications, including antiplatelet and anticoagulant medications
- Record adverse events, device malfunctions and protocol deviations as appropriate
- Query subject for adverse events or hospitalizations since last follow-up and document

### 6.12 Unscheduled Neurology Visit

An **Unscheduled Neurology Visit** may be triggered by any of the following:

- Subject-reported stroke/TIA;
- QVSFS score > 0;
- Subject-reported symptoms; or
- Investigator suspects a stroke during a protocol-required office visit or phone follow-up.

A board-certified study Neurologist blinded to subject’s randomization and implanted device, to the extent possible, must evaluate the following:

- The likelihood that a “yes” answer on the QVSFS or related symptoms are stroke related (this evaluation may be done over the phone or by reviewing available medical records related to a recent neurology exam).
- If there is no question of or concern for a stroke/TIA and an **Unscheduled Neurology Visit** is not required, in the opinion of the study Neurologist, rationale why this visit is not required must be documented.
- If there is any question of or concern for stroke, the subject must have an **Unscheduled Neurology Visit** within 14 days of QVSFS administration or any reported stroke/TIA. At **Unscheduled Neurology Visits** the following must be performed:
  - If stroke is suspected, the NIHSS and mRS (see **Appendix IV: Neurologic Assessments**) must be administered
  - Brain imaging must be performed (MRI unless contraindicated, then CT), unless recent brain imaging (e.g., from emergency department visit at another hospital) is available and deemed adequate by the study Neurologist, at his/her discretion.
  - If stroke is confirmed, appropriate neurology-guided investigations must be conducted to determine stroke etiology (see **Appendix I: Acronyms and Definitions** for stroke definition and etiology). The following is recommended:
    - Cervical/neck artery imaging (CTA/MTA/carotid Doppler)
    - Intracranial artery imaging (CTA/MTA/transcranial Doppler)
    - 24-hour cardiac monitoring
    - Brain imaging (MRI unless contraindicated, then CT)
    - A TEE evaluation is recommended.
      - If a TEE is indicated, perform a TEE following the Echocardiography Protocol to ascertain the mechanism of stroke and submit images to ECL
    - Subject must have a mRS re-administered 90 (+/- 15) days after any confirmed stroke
  - Any imaging files must be made available for CEC review
  - Document location of any intracranial bleeding

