## 1. SYNOPSIS

Trial Title	WAVECREST 2 Trial: W AveCrest V s. Watchman Transsc E ptal LAA Closure to R Educe AF-Mediated S Troke 2
Name of Investigational Device	Coherex WaveCrest ® Left Atrial Appendage Occlusion System
Purpose	To evaluate the safety and effectiveness of the Coherex WaveCrest Left Atrial Appendage Occlusion System
Intended Use	The Coherex WaveCrest Left Atrial Appendage Occlusion System is a percutaneous transcatheter device intended to be used for closure of the left atrial appendage (LAA)
Design	Prospective, multicenter, randomized, active control, clinical trial of the Coherex WaveCrest Left Atrial Appendage (LAA) device compared to the Watchman ® LAA device for the reduction in risk of ischemic stroke or systemic embolism in subjects with non-valvular atrial fibrillation who have an appropriate rationale to seek a non-pharmacologic alternative to chronic oral anticoagulation (OAC).
Blinding	
The following personnel will be blinded to the randomization assignment and treatment received:
 
 
• Neurology personnel evaluating subject, to the extent possible
 
• Clinical Events Committee (CEC) that will adjudicate primary safety and effectiveness events, death (cardiovascular vs. non-cardiovascular), and bleeding category
 
• Investigator’s staff administering the Questionnaire for Verifying Stroke-Free Status (QVSFS), the modified Rankin Scale (mRS), and the National Institutes of Health Stroke Scale (NIHSS) questionnaires
 

Devices Used	Watchman LAA Closure Device and Delivery Sheath WaveCrest Left Atrial Appendage Occlusion System and Delivery Sheath
Subject Population	The subject population will include participants $\geq 18$ years old diagnosed with non-valvular atrial fibrillation and a CHADS 2 score $\geq 2$ or a CHA 2 DS 2 -VASc score $\geq 3$ who have an appropriate rationale to seek a non-pharmacologic alternative to chronic oral anticoagulation.
Definitions	See protocol definitions in Appendix I: Acronyms and Definitions
Primary Effectiveness Endpoint	Composite rate of ischemic stroke or systemic embolism at 24 months

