- The QVSFS must be administered at each follow-up interval (with the exception of the 3-month visit) by a person blinded to the subject’s randomization/implanted device and post-implant medication regimen. The QVSFS can be administered in person, over the phone, and/or at satellite clinical locations. Blinding does not apply to baseline QVSFS administration. There is no special training required to administer this questionnaire. The **Signature and Delegation of Duties Log** may be used to indicate licensed hospital or clinic personnel who are blinded to the subject’s randomization arm or device received to administer the questionnaire. Training of these personnel by the Sponsor will be documented in the **Training Log**.
- The mRS and NIHSS will be administered to all subjects at baseline, if an increase in QVSFS score is observed in a subsequent visit, or if a neurology office consultation is indicated. Blinding does not apply to baseline mRS/NIHSS. Any mRS or NIHSS during follow-up must be administered by a person blinded to the subject’s randomization and implanted device, who has completed requisite training and is listed on the trial **Signature and Delegation of Duties Log** or appropriately documented.
- The board-certified study Neurologist who will assess the subject for primary endpoints will be blinded to the subject’s randomization assignment and implanted device to the extent possible.
- An independent CEC will review and adjudicate events without knowledge of subject’s randomization assignment or implanted device.
- Subjects may withdraw from the trial for any reason, either voluntarily or due to lost-to-follow-up. Adverse events will be reported through the date of subject discontinuation.

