## 4.2 Scope of Trial

The WAVECREST 2 trial is a prospective, multicenter, randomized, active controlled, clinical trial to evaluate the safety and effectiveness of the Coherex WaveCrest Left Atrial Appendage (LAA) Occlusion System for the reduction in rate of ischemic stroke or systemic embolism in subjects with non-valvular atrial fibrillation who are at increased risk for stroke and have an appropriate rationale to seek a non-pharmacologic alternative to chronic oral anticoagulation.

Subjects will be randomized in a 1:1 ratio to the Treatment Arm (Coherex WaveCrest LAA occlusion system) or the Control Arm (Boston Scientific’s Watchman LAA occlusion system). Randomization will be stratified by site and CHA2DS2-VASc score ≤ 4 vs. > 4. The trial is designed to demonstrate that safety and effectiveness of the WaveCrest device are non-inferior to the Watchman device. The subject, the implanting Investigator and catheterization laboratory staff will have knowledge of the assigned treatment. Trial personnel and the board-certified study Neurologist who will perform follow-up assessments for ascertainment of the primary effectiveness endpoint will be blinded to the randomization assignment and implanted device to the extent possible.

An independent Clinical Events Committee (CEC) will be blinded to the treatment assignment and will adjudicate protocol-defined events, including primary and secondary endpoints, death (cardiovascular vs. non-cardiovascular), and bleeding category. An independent Data Monitoring Committee (DMC) will monitor the safety of trial subjects and will review data at interim analyses. The DMC may provide recommendations for early regulatory filing of trial results upon review of interim analyses. An independent Echocardiography Core Laboratory (ECL) will review transesophageal echocardiograms (TEE) to assess LAA closure and device thrombus and will review post-stroke TEEs to ascertain the mechanism of stroke. Transthoracic echocardiograms (TTE) will be assessed by the core lab to assess for post-implant pericardial effusion.

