**18.2 Clinical Event Committee (CEC)**

A Clinical Events Committee (CEC) composed of physicians from different specialties will be appointed by the Sponsor to adjudicate primary effectiveness and safety endpoints, secondary endpoints, death (cardiovascular vs. non-cardiovascular), and bleeding categories. CEC members will not be on the Physician Advisory Committee or Investigators in the trial. The CEC will be composed of at least 4 physicians: 2 stroke Neurologists and 2 Cardiologists. Each CEC meeting will require a quorum. The names of the CEC members, responsibilities of the CEC, the frequency of CEC meetings, the adjudication process and the process for documentation of the adjudication outcome will be specified in a **CEC Charter**. CEC members will be blinded to subject’s randomization assignment and implanted device.

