### 19.1 Echocardiography Core Lab

An Echocardiography Core Laboratory (ECL) will be appointed by the Sponsor to assess TEEs for LAA closure and presence of device thrombus and TTEs for pericardial effusion post-procedure. The ECL will also assess post-stroke TEEs to ascertain the mechanism of stroke. The ECL will provide an ***Echocardiography Protocol*** and training to investigational sites. The responsibilities and processes to be followed by the ECL will be described in an ***ECL Manual of Operations***.

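### Section 6.12 makes all imaging available to the Clinical Events Committee, including any post-stroke TEE that shows the implant, which conflicts with the committee's unqualified blind to the implanted device

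*Protocol*

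**What the plan says.** **Blinding of the CEC.** The protocol declares it in four places.

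- Section 18.2: "CEC members will be blinded to subject’s randomization assignment and implanted device".
- Section 3.7: "An independent CEC will review and adjudicate events without knowledge of" the subject's assignment or implanted device.
- Section 4.2: the committee "will be blinded to the treatment assignment and will adjudicate protocol-defined events".
- Synopsis, Blinding row: the list of blinded personnel includes the "Clinical Events Committee (CEC) that will adjudicate primary safety and effectiveness events", and that list is blinded to both the assignment and the treatment received.

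None of the four softens the blind for the CEC. The neurology personnel, by contrast, are blinded only as far as possible.

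**Imaging.** Section 6.12 requires brain MRI or CT at the visit unless adequate recent imaging exists. If stroke is confirmed, it recommends neck and intracranial artery imaging, cardiac monitoring and a TEE, with the TEE images submitted to the ECL. The list then states: "Any imaging files must be made available for CEC review". No modality is excepted.

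**Core laboratory.** Section 19.1 gives the ECL the TEE reads for closure and device thrombus, and adds: "The ECL will also assess post-stroke TEEs to ascertain the mechanism of stroke". Section 4.2 and the Synopsis say the same in substance.

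**The concern.** Subjects, implanting investigators and catheterization laboratory staff know the arm (section 4.2). Blinded central adjudication is therefore a main protection for the primary effectiveness endpoint, ischemic stroke or systemic embolism at 24 months. Calls such as stroke against TIA, or ischemic against hemorrhagic, involve judgement.

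A site-confirmed stroke is exactly the kind of case that goes to the CEC as a candidate primary event. If its file contains a TEE showing the implant, an adjudicator may learn the arm while making that call. The protocol then promises a blind in one section and prescribes, in another, a step that can break it.

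**Working it through.** No formula applies and the plan gives no figure to reproduce. The check sets the texts side by side.

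1. **Does the imaging rule cover the TEE?** The rule in section 6.12 stands at the level of the visit, not under brain imaging, and it follows the TEE recommendation in the same list. On a plain reading a TEE done at or after the visit is included. The instruction to submit TEE images to the ECL names one recipient but does not exclude the CEC.

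2. **When is there a TEE?** It is recommended, not required, and only after stroke is confirmed. The mandatory imaging is brain MRI or CT, which does not show the left atrial appendage. The exposed cases are therefore site-confirmed strokes in which a TEE was done.

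3. **Does the TEE show the implant?** The Synopsis has the core laboratory read TEEs from neurology evaluations for closure and thrombus. Both reads require the device to be in view.

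4. **Could a reader tell the devices apart?** Section 5.1 describes WaveCrest as a separate occluder and anchors, with ePTFE on the atrial face and foam on the appendage side. Section 5.2 describes Watchman as a self-expanding nitinol structure with a porous PET membrane. Section 18.2 requires at least 2 cardiologists on the CEC. That they could recognise the device is an inference from these descriptions. It is a reasonable one, but the documents do not state it.

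5. **Is there a safeguard?** The visible text contains no masking step, no exclusion of echo images and no device-neutral summary for the CEC. Section 18.2 leaves the adjudication process to a CEC Charter that was not supplied, and parts of the SAP are redacted. A safeguard can be called not visible, but not absent.

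6. **Does the CEC need the TEE for the primary effectiveness event?** Appendix I defines ischemic stroke by a sudden deficit in a vascular territory, its duration, and a relevant lesion on neuroimaging or a visualized retinal infarct. TEE is not a criterion. It bears on mechanism, which feeds the descriptive endpoint of cardioembolic stroke (section 15.6). Withholding raw TEE images costs the primary endpoint nothing.

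**The case against.** The strongest reply is that making files available does not mean that adjudicators view raw, unmasked TEEs. The ECL is the named recipient and reader, and the Charter may already provide for masking. This stands as far as it goes: the documents do not show that the blind fails in practice. It does not remove the conflict, because section 6.12 states an unqualified duty beside an unqualified blind, and a site following it as written would hand over the TEE.

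A second reply is that the TEE is optional, comes only after a confirmed stroke and is not part of the stroke definition. The first two parts limit the exposure. The third supports the fix.

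Several stronger readings are tempting, and the documents do not support them.

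- *The blind on the primary endpoint cannot hold.* This would need evidence that the CEC sees unmasked TEEs and recognises the device. Neither is stated.
- *No blinded layer is left.* Follow-up QVSFS, mRS and NIHSS are administered by blinded staff, and the study neurologist is blinded as far as possible (section 3.7).
- *Both primary endpoints are compromised.* Section 6.12 covers neurology visits. It does not send the CEC imaging for effusions, vascular complications or most bleeding.
- *Medication records also unblind the CEC.* Section 3.7 blinds QVSFS staff to the subject's "randomization/implanted device and post-implant medication regimen", and its sentence on the CEC does not mention regimen. But no section says that the CEC receives medication records, and the Synopsis already blinds it to the treatment received. Regimen is also an imperfect marker: by Table 3, from 6 months both arms are on aspirin alone unless warfarin continues for non-closure.
- *The bias can be put in figures.* Any reclassification rate would be invented, and nothing in the documents gives its direction.

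**Conclusion.** The point holds as a conflict between two stated rules, not as a demonstrated failure of blinding. Followed as written, section 6.12 can put images of the implant before adjudicators who are declared blind to it in sections 3.7 and 18.2.

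The conclusion rests on two assumptions: that the imaging rule means what it plainly says, and that a cardiologist could probably distinguish the devices on TEE. It is also conditional on the Charter, which might already resolve the matter.

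The number of affected cases cannot be derived, because the documents do not say how often the recommended TEE will be done. The correction is worth making because the affected cases are candidate primary events and the change is cheap.

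**What to change.** Replace the sentence in section 6.12 with wording such as: *Brain and vascular imaging files are made available to the CEC. TEE and TTE images are sent only to the ECL, which gives the CEC a device-neutral report stating device thrombus (yes or no), gap size, effusion and any other cardiac source.* Align the CEC Charter with this text, and require any accidental unblinding of a CEC member to be recorded.

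The ECL already reads post-stroke TEEs, so no new assessment is needed. The cost is some extra document handling, and the CEC would rely on the ECL's read for the descriptive cardioembolic classification. If the Charter already contains an equivalent step, only the sentence in section 6.12 needs to change to match it.
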